
 • To evaluate the use of rescue treatment and changes in concurrent ITP therapy while receiving treatment with efgartigimod PH20 SC compared to placebo PH20 SC 	
 • Rate of receipt of rescue therapy (rescue per patient per month) in the overall population • Proportion of patients for whom dose and/or frequency of concurrent ITP therapies have increased at week 12 or later in the overall population

 • To evaluate the effects of efgartigimod PH20 SC treatment on QoL measures and PRO compared to placebo PH20 SC 	
 • Change from baseline in PRO (Functional Assessment of Chronic Illness Therapy Fatigue Scale [FACIT-Fatigue], Functional Assessment of Cancer Therapy questionnaire-Th6 [Fact-Th6]) and QoL (Short Form-36 [SF-36]) at planned visits in the overall population

 • To assess the immunogenicity of efgartigimod and rHuPH20 	
 • Incidence and prevalence of antibodies to efgartigimod and/or rHuPH20 in the overall population • Titers of antibodies to efgartigimod and/or rHuPH20 in the overall population • Presence of neutralizing antibodies (NAb) against efgartigimod and/or rHuPH20, and titers of NAb against rHuPH20 in the overall population

 • To assess the PK of efgartigimod PH20 SC 	
 • Serum efgartigimod concentration observed predose (C_{trough}) in the overall population

To assess the PD effects of efgartigimod PH20 SC	
Pharmacodynamics markers: total IgG and antiplatelet antibody levels in the overall population
Exploratory	

[REDACTED]	
[REDACTED]

[REDACTED]	
[REDACTED]

[REDACTED]	
[REDACTED]

[REDACTED]	
[REDACTED]

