6.6.1. Concurrent ITP Therapy

- Participants receiving at least 1 permitted concurrent ITP therapy are eligible for the trial, if the dose and schedule have remained unchanged in the last 4 weeks before randomization (ie, visit 1).
- Permitted concurrent ITP medications include corticosteroids, danazol, vinca alkaloids, oral immunosuppressants, dapsone, fostamatinib, and/or oral TPO-RAs (see inclusion criterion 7, Section 5.1).
- Dose and frequency of permitted concurrent ITP therapies should remain unchanged during the trial.

- Exceptions are participants who are receiving concurrent treatment with oral TPO-RAs in whom dose changes are permitted at label-defined platelet thresholds, and participants who are receiving concurrent treatment with fostamatinib, in whom dose changes or stopping of treatment is allowed in label-defined conditions.
- As of week 12, the start or an increase in the dose and/or schedule of permitted concurrent ITP therapy is allowed for participants who have an “insufficient response” (ie, no platelet count of $\geq 30 \times 10^9/L$ in any of the visits during the last 4 weeks). These participants will be considered as “nonresponders” for the primary endpoint analysis. At the discretion of the investigator, the dose and/or schedule of the concurrent ITP therapy can be returned to the baseline levels.
- Participants not receiving concurrent ITP therapy are also eligible for the trial (see inclusion criterion 7, Section 5.1). The washout periods as specified in exclusion criteria 2 to 8 must be followed. See also Section 10.4.
- Any change in concurrent ITP therapy should appropriately be recorded on the eCRF.
- The medical monitor at the sponsor’s designated CRO should be contacted if there are any questions regarding concomitant or prior therapy.

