1.2 STUDY ENDPOINTS

1.2.1 *Primary endpoint*

The primary endpoint is the proportion of patients with chronic ITP with a sustained platelet count response defined as achieving platelet counts of at least $50 \times 10^9/L$ for at least 4 of the 6 visits between week 19 and 24 of the study.

Participants who discontinue treatment prior to visit 24 due to lack of efficacy (e.g. more than 3 occurrences of rescue therapy) or due to an AE, and who have not achieved sustained platelet count response between week 19 and 24, are considered non-responders. Participants who receive rescue therapy at week 12 or later, or for whom dose and/or frequency of concurrent ITP therapies have increased at week 12 or later, are also considered non-responders.

1.2.2 *Secondary endpoints*

Key Secondary Efficacy Endpoints Subject to Alpha Control:

- Extent of disease control defined as the number of cumulative weeks over the planned 24-week treatment period with platelet counts of $\geq 50 \times 10^9/L$ in the chronic ITP population.
- Proportion of patients in the overall population (chronic and persistent ITP) with a sustained platelet count response defined as achieving platelet counts of at least $50 \times 10^9/L$ for at least 4 of the 6 visits between week 19 and 24 of the study.
- Proportion of patients in the overall population achieving platelet counts of at least $50 \times 10^9/L$ for at least 6 of the 8 visits between week 17 and 24 of the study.
- Incidence and severity of the WHO-classified bleeding events in the overall population.

Other Secondary Endpoints Not Subject to Alpha Control (overall population):

- Proportion of patients with overall platelet response defined as achieving a platelet count of $\geq 50 \times 10^9/L$ on at least 4 occasions at any time during the 24-week treatment period.
- Extent of disease control defined as the number of cumulative weeks until week 12, with platelet counts of $\geq 50 \times 10^9/L$.

	Statistical Analysis Plan	
ARGX-113-2004	Final analysis	Final 1.0 of 7NOV2023

- Proportion of patients with overall platelet response defined as achieving a platelet count of $\geq 50 \times 10^9/L$ on at least 4 occasions at any time until week 12.
- Mean change from baseline in platelet count at each visit.
- Time to response defined as the time to achieve 2 consecutive platelet counts of $\geq 50 \times 10^9/L$.

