- The number of cumulative weeks over the planned 24-week treatment period with platelet counts $\geq 30 \times 10^9/L$ and at least $20 \times 10^9/L$ above baseline.
- In patients with baseline platelet count of $< 15 \times 10^9/L$, the number of cumulative weeks over the planned 24-week treatment period with platelet counts of $\geq 30 \times 10^9/L$ and at least $20 \times 10^9/L$ above baseline.
- Proportion of patients with an IWG response
- Proportion of patients with and IWG complete response
- Proportion of patients with an initial response
- Rate of receipt of rescue therapy (rescue per patient per month).
- Proportion of patients for whom dose and/or frequency of concurrent ITP therapies have increased at week 12 or later.
- Change from baseline in PRO (Functional Assessment of Chronic Illness Therapy [FACIT-Fatigue], Functional Assessment of Cancer Therapy questionnaire-Th6 [FACT-Th6]) and QoL (SF-36) at planned visits.
- Incidence and prevalence of antibodies to efgartigimod and rHuPH20.
- Titers of antibodies to efgartigimod and rHuPH20.
- Presence of neutralizing antibodies (NAb) against efgartigimod and rHuPH20, and titers of NAb against rHuPH20.
- Pharmacokinetic parameters of efgartigimod: serum efgartigimod concentration observed predose (C_{trough}).
- Pharmacodynamics markers: Total IgG and antiplatelet antibody levels.

Safety Evaluation:

- Incidence and severity of treatment-emergent adverse events (AEs), adverse events of special interest (AESIs), and serious adverse events (SAEs).
- Vital signs (VS), electrocardiogram (ECG), and laboratory assessments.

Exploratory Endpoints:

- [REDACTED]
- [REDACTED]
- [REDACTED]
- [REDACTED]

	Statistical Analysis Plan	
ARGX-113-2004	Final analysis	Final 1.0 of 7NOV2023

- [REDACTED]
- [REDACTED]

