3.5 PRIOR AND CONCOMITANT THERAPIES

3.5.1 Available data

All therapies are coded using the WHO-DRUG Dictionary version MAR2023 (Global) Format B3. Anatomical therapeutic chemical (ATC) selection is performed. The ATC coding up to level 4 is available in the clinical database. For each therapy, a start date or prior flag and stop date or ongoing flag are collected.

	Statistical Analysis Plan	
ARGX-113-2004	Final analysis	Final 1.0 of 7NOV2023

3.5.2 *Derivation rules*

Based on their start and stop date, therapies will be allocated into 1 or both of the following categories:

- Prior: any therapy that strictly started before the first IMP dose date.
- Concomitant: any therapy that was taken on or after the first IMP dose date.

A medication that started before the first IMP dose date and continued during the study will be classified as both prior and concomitant.

The ITP-specific therapies will be allocated to the following categories:

- Prior ITP therapy: stopped prior to first IMP dose date
- Continued concurrent ITP therapy: started prior to first IMP dose date and continued on or after first IMP dose date
- New concurrent ITP therapy: started on or after first IMP dose date or therapy of which the mean daily dose has increased compared to baseline

ITP therapy records with the same equivalent name will be combined to do the allocation in case the end and start date overlap or are subsequent, the start date of the next record being one day after the end date of the current record. For the combination of records, records with (partially) missing dates will be excluded. Therapies with (partially) missing dates will be allocated to each category unless the available parts of the therapy start or stop date or the started prior to trial/ongoing at end of trial flag provide evidence not to do so.

The type of ITP therapy will be allocated to the following categories according to the medical review performed by the sponsor: corticosteroids / IVIG, anti-D / fostamatinib / splenectomy / TPO-RA/ dapsone / danazol / anti-CD20 / other immunosuppressants. Therapies that cannot be assigned to any of these 9 categories will be categorized to type 'Other'.

Rescue ITP therapy will be allocated to the following categories:

- methylprednisolone, dexamethasone, prednisolone, prednisone: selection based on ATC4 = "H02AB"
- immunoglobulins given IV (IVIg): selection based on ATC4 = "J06BA"

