4.1.2.1 PRIMARY ENDPOINT

The primary endpoint is the proportion of participants with a sustained platelet count response (week 19 – 24) within the adult population with chronic ITP.

A participant is considered a responder, ie, has a sustained platelet count response, if he/she shows platelet counts of at least $50 \times 10^9/L$ for at least 4 of the 6 analysis visits between weeks 19 and 24 of the study. ($\geq 50 \times 10^9/L$ prim resp).

The main analysis on the primary endpoint will use the ‘composite variable strategy’ in case of main intercurrent events using the Cochran-Mantel-Haenszel test (see also section 4.1.3.2). This strategy implies that when a main intercurrent event occurs, a participant is considered a non-responder, if the participant has not achieved sustained platelet count response before the occurrence of the main intercurrent event. This happens in the following situations:

- early discontinuation of treatment (prior to week 24) due to lack of efficacy (DSDECOD = “Lack of efficacy”) or due to an AE
- initiation of rescue therapy at week 12 or later: relative day of start date of rescue medication \geq lower limit ADY of analysis visit corresponding to Week 12

	Statistical Analysis Plan	
ARGX-113-2004	Final analysis	Final 1.0 of 7NOV2023

- increase of dose and/or frequency of concurrent ITP therapies or start of a new concurrent ITP therapy at week 12 or later:
 - (if start date concurrent ITP therapy \geq lower limit ADY of analysis visit corresponding to Week 12) and (dose > previous dose of the specific ITP therapy OR frequency > previous frequency of the specific ITP therapy)
 - AND
 - (if start date concurrent ITP therapy \geq lower limit ADY of analysis visit corresponding to Week 12) and (dose > dose of the specific ITP therapy at baseline OR frequency > frequency of the specific ITP therapy at baseline)
 - OR
 - new ITP therapy

Note: if for frequency a change is detected, but it is not clear whether a real increase has taken place, it will be considered worst-case and analysed as increase (e.g.: Baseline value 'QD' changed to e.g. 'at will', 'as needed'; Baseline value 'As needed' changed to e.g. 'QD', 'continuous'). Dose and frequency will always be considered in combination (ie, mean daily doses will be compared).

Missing values for reasons other than the main intercurrent events, will be imputed as described in section 4.1.2.5 (approach 1).

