ARGX-113-2004	Final analysis	Final 1.0 of 7NOV2023

- Scale score = mean of all available converted item scores
A scale score cannot be calculated if less than 50% of the items of the scale are answered. Otherwise, scores for missing items will be imputed with the arithmetic average of the non-missing item scores. Converted item scores are not rounded when calculating the scale score.

- 6) Rate of receipt of rescue therapy: number of times rescue therapy is given per month, calculated as $\frac{\text{Total number of occurrences}}{\text{total days in treatment phase}} \times 30.4$

Occurrence: a period of maximum 5 days where 1 or more rescue treatments are administered simultaneously or consecutively to the study participant. The start date/time of the occurrence is the start of the administration of the first rescue treatment. If this period exceeds the maximum of 5 days, a new occurrence will be assigned, with start date/time of the occurrence being the start date 5 days after the initial occurrence start date.

- 7) Proportion of participants for whom dose and/or frequency of concurrent ITP therapies have increased at week 12 or later.

Derivation: a participant is counted if (start date concurrent ITP therapy \geq lower limit ADY of analysis visit corresponding to week 12) AND (dose > previous dose of the specific ITP therapy OR frequency > previous frequency of the specific ITP therapy OR new ITP therapy). Note: Dose and frequency will always be considered in combination (ie, mean daily doses will be compared).

- 8) Time to platelet count response defined as the time to achieve 2 consecutive platelet counts of $\geq 50 \times 10^9/L$.

Derivation: It will be calculated as the difference between the first assessment date at which the condition '2 consecutive platelet counts $\geq 50 \times 10^9/L$ ' is fulfilled, taking into account all platelet count measurements (also the unscheduled ones), and first IMP intake date.

Time to platelet count response (days) = date (first assessment) – first IMP date + 1:

Table 9: Definition for Time to Platelet Count

Response Situation	Time to Platelet Count Response	Outcome ^d
No occurrence of platelet count of $\geq 50 \times 10^9/L$	Date of last available platelet count ^c – first IMP date ^b + 1	Censored
Early discontinuation of treatment (prior to W24) due to lack of efficacy or due to AE ^a	Early treatment discontinuation date – first IMP date ^b + 1	Censored

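### SAP 4.1.2.3 item 7 counts a concurrent ITP therapy as increased without comparing it with baseline, so a reduced dose that is later restored, fully or partly, counts as an increase

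*SAP*

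**What the plan says.** Protocol section 3 lists the secondary endpoint as "Proportion of patients for whom dose and/or frequency of concurrent ITP therapies have increased at week 12 or later in the overall population". SAP 1.2.2 repeats it: "Proportion of patients for whom dose and/or frequency of concurrent ITP therapies have increased at week 12 or later". Neither names the level against which an increase is measured.

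SAP 4.1.2.3 item 7 supplies the derivation. The record must start on or after the lower limit of the week-12 analysis window, and it must satisfy "dose > previous dose of the specific ITP therapy OR frequency > previous frequency of the specific ITP therapy OR new ITP therapy". A note adds that dose and frequency are combined into a mean daily dose before comparison.

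SAP 1.2.1 uses nearly the same phrase for primary non-response: participants "for whom dose and/or frequency of concurrent ITP therapies have increased at week 12 or later, are also considered non-responders". SAP 4.1.2.1 derives that event under the lead line "increase of dose and/or frequency of concurrent ITP therapies or start of a new concurrent ITP therapy at week 12 or later". It sets the same comparison with the previous record and joins to it, by AND, a second requirement: "dose > dose of the specific ITP therapy at baseline OR frequency > frequency of the specific ITP therapy at baseline".

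SAP 3.5.2 also measures against baseline. Its category of new concurrent ITP therapy includes a "therapy of which the mean daily dose has increased compared to baseline".

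Protocol 6.6.1 keeps concurrent therapy unchanged by default, but: "Exceptions are participants who are receiving concurrent treatment with oral TPO-RAs in whom dose changes are permitted at label-defined platelet thresholds". For fostamatinib it allows dose changes or stopping under label-defined conditions.

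**The concern.** One phrase has two derivations in the same SAP. For the primary endpoint, an increase means above the previous record and above baseline. For the secondary endpoint, it means above the previous record only. SAP 6.1, as far as it is readable, gives no reason for the difference.

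The difference matters only for a dose that goes down and then up, and Protocol 6.6.1 makes that sequence possible within protocol. A participant whose TPO-RA dose is halved and later returned to its starting level is on no more background therapy than at entry, yet item 7 reports an increase. A dose raised only part of the way back is reported the same way while still below baseline.

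At stake is the reading of one secondary endpoint. A table that appears to show participants who went onto more background therapy would also contain participants who returned towards the level they started on. For participants with chronic ITP, it could also disagree with the intercurrent-event table.

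**Working it through.** The plan states no figure for this endpoint, so there is none to reproduce. The check applies both rules to the same dose histories.

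**Date limit.** SAP Table 4 gives week (4 + x) a lower limit of 26 + 7x, a target of 29 + 7x and an upper limit of 32 + 7x. For week 12, x = 8: lower limit 26 + 56 = day 82, target 29 + 56 = day 85, upper limit 32 + 56 = day 88.

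**The rules.** Let D be the mean daily dose of the new record, P that of the previous record and B that at baseline. The new-therapy branch is left out of both.

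- Item 7: start day ≥ 82 and D > P.
- 4.1.2.1: start day ≥ 82 and D > P and D > B.

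They differ exactly when P < D ≤ B. Because 4.1.2.1 lists the previous level and the baseline level as separate conditions, *previous* cannot be read as *baseline*.

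**Grid check.** Take dose levels of 25%, 50%, 100%, 150% and 200% of baseline, with the change on or after day 82. There are 5 × 4 = 20 possible changes. Item 7 counts the 10 upward ones. The 4.1.2.1 rule counts 7: three that end at 150% and four that end at 200%. The 3 extra under item 7 are 25% to 50%, 25% to 100% and 50% to 100%. None exceeds baseline.

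**Illustrative histories** (assumed baseline of 50 units):

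| History | Item 7 | 4.1.2.1 |
|---|---|---|
| No change | no | no |
| 25 on day 60, 50 on day 90 | yes | no |
| 25 on day 60, 37.5 on day 90 | yes | no |
| 25 on day 90, 50 on day 120 | yes | no |
| 25 on day 60, 50 on day 75 | no | no |
| 25 on day 60, 50 on day 82 | yes | no |
| 75 on day 90 | yes | yes |
| 25 on day 60, 75 on day 90 | yes | yes |

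Item 7 counts 6 of 8 and 4.1.2.1 counts 2 of 8. The 4 that differ are all full or partial restorations on or after day 82. With the baseline condition added, those 4 drop out and both true increases stay.

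**Does other text supply the missing condition?** The mean-daily-dose note merges dose with frequency but leaves the comparator as the previous record. The baseline reference in 3.5.2 could enter item 7 only through the new-therapy branch. That branch is joined by OR, so it can add participants but cannot remove a restored dose.

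**The new-therapy branch.** SAP 3.5.2 combines records of the same therapy only when they overlap or follow on consecutive days, and it treats a therapy started on or after first dosing as new. If item 7 takes that meaning, a baseline therapy stopped and restarted after a gap, at its baseline dose and on or after day 82, would count as new. A baseline condition on the dose branch alone would not remove it.

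**Weight of one participant.** At the planned maximum of 180 + 39 = 219 randomized 2:1, the arms are 219 × 2/3 = 146 and 219 × 1/3 = 73. One participant counted this way adds 1/146 = 0.68 percentage points in the efgartigimod arm or 1/73 = 1.37 in the placebo arm. How many there would be is unknown.

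**The case against.** The best defence is that item 7 is a choice, not a mistake. The protocol endpoint names no reference level, and a record above the one before it has literally increased. The parent objective speaks of changes in concurrent therapy, and Table 14.2.6.1 is titled as a change in ITP therapy. The two rules also serve different ends: one turns a participant into a non-responder, the other feeds a descriptive table. The rule is prespecified and programmable, and the listing of concurrent ITP therapies will show every record.

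Much of this stands as a limit on importance. It does not remove the inconsistency. Where the SAP gives this wording an operational meaning elsewhere, in 4.1.2.1 and 3.5.2, it refers to baseline, and no reason is given for a second meaning.

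It is also fair that Tables 14.2.6.1 and 14.2.7.1 cover different populations (overall and chronic), so their totals would differ anyway. The conflict is at participant level, among those with chronic ITP.

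A reader might infer that the last branch of 4.1.2.1 lets a new therapy begun before week 12 count as a primary intercurrent event, or that Table 8 has lost its date limit. The documents do not support this as a defect: the lead line of the 4.1.2.1 event already carries the week-12 date, and 4.1.2.2 refers this event back to 4.1.2.1.

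**Conclusion.** Wrong as written, low priority. Item 7 counts as increased any dose or frequency that rises from the previous record on or after day 82, including rises that end at or below baseline. The SAP's own rule for the same-worded primary event does not. This rests on the text of the two derivations and on dose reductions and restorations being possible under Protocol 6.6.1. Restorations before day 82 are not affected.

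The reach is small. The endpoint is outside alpha control, only a frequency tabulation is planned in SAP 4.1.3, and the primary analysis already has the baseline condition.

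A reader might infer a sizeable bias against efgartigimod, on the reasoning that platelet counts rise more in that arm, TPO-RA doses are cut there and some are later restored. The direction is plausible, because Protocol 6.6.1 ties TPO-RA changes to platelet thresholds, but it remains an assumption. The documents do not say how many participants take an oral TPO-RA or fostamatinib, how many would be reduced, or how many would be raised again after day 82. No share of either arm, and no shift in the between-arm difference, can be estimated.

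**What to change.** In SAP 4.1.2.3 item 7:

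1. Add to the dose and frequency conditions: *AND mean daily dose > baseline mean daily dose of the specific ITP therapy*.
2. State that, for item 7, restarting a therapy in use at baseline is judged by this baseline comparison and is not counted as new.

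Leave the primary rule in 4.1.2.1 and Table 8 unchanged. Redefining *new* in 4.1.2.1 could reclassify participants for the primary endpoint, which this point does not justify. One difference may remain: if the undefined term in 4.1.2.1 is programmed from the 3.5.2 category, a restart after a gap would be an intercurrent event there but not an increase in item 7. A footnote to Table 14.2.6.1 can say so.

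If any rise from the previous record really is what the sponsor wants, the alternative is to say so in item 7 and label the table accordingly.

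The cost is one condition and one sentence in a single derivation, using concomitant-medication data already collected. The downside is that fewer participants may be counted as increased.
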